### ***Data Collection Strategy and Sources***

Data will be collected using two strategies to best integrate data available from routine care within the electronic health record and daily routine activities of the hospital pharmacist: electronic data and data manually entered into a REDCap database.

Electronic Data - The majority of data will come from existing datasets collected as part of clinical operations. Electronic data extracts will be prepared from each hospital's electronic systems according to a pre-specified data dictionary for each of the primary and secondary outcomes and additional data outlined above. The primary outcome will be measured directly from electronic medication administration records (eMAR) which captures the location, administration date/time, and agent used. Additional endpoints will be extracted from billing, administrative, and laboratory data and will emulate files previously collected for DETOURS-Retro (Pro00076818). Key difference in data collected with the trial as opposed to DETOURS-Retro is that datasets for this trial will include PHI including MRN in order to adequately link outcomes captured in electronic data extracts with manually collected data.

REDCap Data – Data specifically collected on eligible patients (Pass Step 1 of Opt-Out Protocol) will be entered into a REDCap database. Data collected from eligible patients will include the result of the Safety Checklist (Step 2) and indication(s) for failure if applicable. For patients who pass the Safety Checklist, additional data will be entered for the result of the Opt-Out Procedure (Step 4) among patients randomized to intervention. Finally, rationale for opt-out will be entered for applicable patients (Step 5). These data, including proportion of eligible patients randomized to intervention and result of Opt-Out Procedure, will be regularly analyzed and fed back to sites as the study progresses.

Institutions will be able to decide for themselves what is the most effective way to document reviews and interventions.

### ***Blinding***

Study personnel and pharmacists will remain blinded to randomization status until Step 3 of the Opt-Out Procedure. In other words, the determination for eligibility and application of the Safety Check will occur prior to knowledge of randomization. No further blinding of study personnel will occur as this is an active, quality-improvement activity that utilizes front-line clinical personnel. No contact with individual patients is anticipated.

### ***Data Monitoring***

No formal interim analyses involving hypothesis testing is planned. Safety outcome monitoring is outlined below (Section 7).

## **5.2 Other Study Procedures**

We will enroll patients as part of this protocol but will seek a waiver of informed consent. Screening and enrollment/baseline are described above. No specific follow-up with patients will occur following hospital discharge. Therefore, the following sections are not applicable:

1. Follow-up
2. Final study visit
3. Follow-up safety phone call
4. Early termination visit
5. Unscheduled visit
6. Laboratory evaluations

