##### **3.1.3 Secondary Objectives**

To determine if the DETOURS opt-out protocol for antibiotic de-escalation will lead to improvement in DOOR among eligible patients identified with suspected sepsis.

To determine if the DETOURS opt-out protocol for antibiotic de-escalation will lead to reduction in *C. difficile* infections among eligible patients identified with suspected sepsis.

To determine if the DETOURS opt-out protocol for antibiotic de-escalation will lead to change in patient outcomes among eligible patients identified with suspected sepsis, including in-hospital mortality, length of stay, and subsequent ICU transfer compared to eligible patients in control units.

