**Table 3. DETOURS Desirability of Outcome Ranking (DOOR) Outcome**

Outcome	Rank
Alive	1
Readmission, relapse of suspected sepsis, C. difficile infection, OR deep venous thrombosis	2
≥2 of items in Rank 2 above	3
Subsequent ICU Admission OR hemodialysis	4
Subsequent ICU Admission AND hemodialysis	5

Death	6
-------	---

*Secondary endpoints:*

- 1) DOOR/RADAR, according to criteria developed in DETOURS-Retro (Pro00076818; Table 3). See Section 7 for definitions of these and other outcomes.
- 2) Safety outcomes potentially related to antibiotic treatments:
  - a. Individual clinical outcome components in the DOOR (Table 3)
  - b. Number of hospital days within 30-days post-randomization
  - c. Re-initiation of antibiotic therapy after >48 hours of no antibiotics within 30-days post-randomization
  - d. Need for new PICC line insertion within 30-days post-randomization
  - e. Central line days within 30-days post-randomization.
- 3) Process indicators:
  - a. Percent of eligible patients with antibiotic de-escalation by day 5, according to an electronic definition of de-escalation
  - b. Of those patients eligible for assessment of de-escalation per the Safety Checklist:
    - i. Number of eligible patients in whom the safety screen was applied.
    - ii. Number patients the safety screen excluded from the opt-out procedure
    - iii. Number of eligible patients in whom the opt-out procedure was employed
    - iv. Number of eligible patients in whom the prescriber chose to opt-out
      1. Prescriber type (e.g. physician, APC, trainee, specialty service consultant (e.g. infectious diseases))
      2. Prescribers' reported rationale for opting out
  - c. Percent of subjects who received an infectious disease consultation after implementation of the Opt-Out
- 4) Days of therapy for specific sub-groups of patients, including patients whose physicians elected to opt-out of the intervention, and sub-groups of hospitals (e.g., community vs. tertiary care hospitals).
- 5) Total days of therapy for each patient, defined as a sum of inpatient days of therapy and projected outpatient days of therapy, as per discharge prescriptions.
- 6) Length of therapy (LOT), defined as the number of days during which the patient receives one or more antibiotics. Repeat primary outcome and secondary outcomes #4 and #5 with LOT.

*Additional Descriptive Data*

We will obtain the following data from each of the patients eligible for the Opt-out protocol:

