## 7 ASSESSMENT OF SAFETY

All randomized patients will undergo safety evaluation.

1. Specifications of safety parameters –Data will be collected on the adverse outcomes described in the Desirability of Outcome Ranking (DOOR) in Table 3 and three other safety outcomes:
  - a. C. difficile infection (CDI) – positive *C. difficile* stool test during the 30 days following randomization. Results from either PCR or ELISA tests are acceptable
  - b. Clinically significant deep venous thrombosis (DVT) – diagnosis of a new DVT during the 30 days following randomization that requires anticoagulation. A radiographic finding (via ultrasound, CT, or MRI) will be required for this diagnosis.
  - c. Readmission – return to the hospital within 30 days of hospital discharge
  - d. Relapse of suspected sepsis – restart or escalation of antibiotic therapy coupled with repeat blood cultures (+/- 24 hours of changed in antibiotic therapy) during the 30 days following randomization.
  - e. Acute kidney injury requiring hemodialysis – new onset acute kidney injury requiring 1 or more hemodialysis sessions during the 30 days following randomization.
  - f. Transfer to Intensive Care Unit (ICU) – admission or transfer to any intensive care unit within 30 days of randomization.
  - g. Death – within 30 days of randomization.
  - h. Number of hospital days (Length of Stay) starting on the day of randomization and up to 30 days post randomization.
  - i. Re-initiation of antibiotic therapy after >48 hours of no antibiotics within 30 days of randomization.
  - j. Need for new PICC line insertion within the 30 days of randomization.
2. Methods and timing for assessing, recording, and analyzing safety parameters – Local study personnel will be responsible for assessing and recording safety parameters. Duke study personnel will be responsible for monitoring safety through interaction with study site PIs and the Independent Monitor.
3. Guidelines for determining causality – causality will not be assessed, as the DOOR outcome is intended to reflect global patient outcomes.
4. Reporting procedures (for AE) – all safety parameters will be entered into the REDCap database. Data on safety parameters will be reviewed by the Independent Monitor and discussed with the central study team.

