### COLLECTION AND REPORTING OF SAEs AND AEs

For this study, the following standard AE definitions are used:

**Adverse event:** Any unfavorable and unintended sign (including an abnormal laboratory finding), symptom or disease temporally associated with the use of a medical treatment or

procedure, regardless of whether it is considered related to the medical treatment or procedure.

**Serious Adverse Event:** Any AE that results in any of the following outcomes:

- Death
- Life-threatening
- Event requiring inpatient hospitalization or prolongation of existing hospitalization
- Persistent or significant disability/incapacity

AEs are graded according to the following scale:

**Mild:** An experience that is transient, & requires no special treatment or intervention. The experience does not generally interfere with usual daily activities. This includes transient laboratory test alterations.

**Moderate:** An experience that is alleviated with simple therapeutic treatments. The experience impacts usual daily activities. Includes laboratory test alterations indicating injury, but without long-term risk.

**Severe:** An experience that requires therapeutic intervention. The experience interrupts usual daily activities. If hospitalization (or prolongation of hospitalization) is required for treatment it becomes an SAE.

AEs are identified by chart review after 30-days post randomization for the 30-day time period following randomization. SAEs and specific procedure-associated AEs are reported to the PI and co-investigators within 24 hours. In addition, all AEs are reported according to the Duke IRB AE reporting guidelines.

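### Death and most DOOR and safety events are defined to day 30 but after discharge are found only through records; the protocol also names two mortality definitions and mismatched readmission and review windows

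*Protocol*

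**What the plan says.** Four parts of the protocol bear on this point.

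- **Outcome windows.** Section 7 gives "Death – within 30 days of randomization" and uses the same 30-day span from randomization for *C. difficile* infection, DVT, relapse, dialysis and admission to an ICU of any kind. Readmission alone is counted to 30 days after discharge. Appendix 4 repeats these definitions.
- **Objective.** Section 3.1.3 lists patient outcomes "including in-hospital mortality, length of stay, and subsequent ICU transfer compared to eligible patients in control units".
- **Contact.** Section 5.2 says "No specific follow-up with patients will occur following hospital discharge" and marks the safety phone call as not applicable. Section 5.1, under Blinding, says "No contact with individual patients is anticipated".
- **Sources.** Section 5.1 says "Additional endpoints will be extracted from billing, administrative, and laboratory data", prepared from each hospital's own systems. Appendix 4 says "AEs are identified by chart review after 30-days post randomization for the 30-day time period following randomization"; the local study monitor does the 30-day chart reviews.

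Table 3 ranks patients from Alive (1, best) to Death (6). Section 9.4.1 compares the arms on this ranking with a Wilcoxon rank-sum test, and its ITT population is all randomized patients.

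**The concern.** The outcome definitions run past discharge without restriction to the study hospital, but the named sources are the hospitals' own extracts and a local chart review. No source is named for a death at home or an ICU stay elsewhere. Such an event may leave no trace, and a patient without a recorded event has no place in Table 3 other than rank 1.

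This matters because the trial tests stopping antibiotics early, and Section 3.1.1 hypothesizes equivalent mortality and ICU transfer. Missed events move absolute differences toward that hypothesis. Relapse and re-initiation of antibiotics, the harms closest to early stopping, are exposed in the same way. The record-only part of the window begins at discharge, and length of stay is itself an outcome that could differ by arm. The Independent Monitor's table in Appendix 4 lists the same outcomes, and its results may be passed to clinicians as reassurance.

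**Working it through.** The protocol gives no event rate, loss to follow-up or DOOR power, so there is no figure of its own to reproduce. The first two steps follow from the text. The later steps are illustrations, and their inputs are assumptions.

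**1. Mortality.** Section 3.1.3 limits mortality to the hospital stay. Section 7 and Appendix 4 do not. A death on day 12 after discharge on day 4 counts under the second definition and not under the first.

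**2. Windows.** Let L be the days from randomization to discharge.
- Part of the 30-day window seen only through records = 30 − L. For L = 4 this is 26 days; for L = 10 it is 20 days. A shorter stay leaves a longer record-only part.
- The readmission window ends on day L + 30 and the chart review covers to day 30, so L days are unreviewed. For L = 4 these are days 31 to 34; for L = 10, days 31 to 40.

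**3. Equal loss, single event.** If a share m of events is missed in both arms, the observed difference is (1 − m) × the true difference. The risk ratio is unchanged, because (1 − m) cancels. With m = 20%, 80% of the true absolute difference is seen.

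**4. Equal loss, DOOR.** P(better) = P(rank in intervention < rank in control) + 0.5 × P(tie), on the clinical ranks alone, without any adjustment for antibiotic duration. Assumed ranks 1 to 6: control 72/16/3/5/1/3%, intervention 66/19/4/6/1/4%.
- Better: 0.66×0.28 + 0.19×0.12 + 0.04×0.09 + 0.06×0.04 + 0.01×0.03 = 0.2139.
- Ties: 0.4752 + 0.0304 + 0.0012 + 0.0030 + 0.0001 + 0.0012 = 0.5111; half is 0.2556.
- True P(better) = 0.469.

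If a share m of patients with events in each arm is moved to rank 1:

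| m | 10% | 20% | 30% | 40% | 50% |
|---|---|---|---|---|---|
| P(better) | 0.473 | 0.476 | 0.479 | 0.482 | 0.485 |

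The assumed harm drifts toward 0.50.

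**5. Unequal loss, DOOR.** Give both arms the control distribution, so the truth is 0.500. Miss 20% of events in control and 25%, 30% or 40% in intervention: P(better) becomes 0.507, 0.514 or 0.528, a spurious benefit. Reversing the loss would give a spurious harm.

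**6. Deaths.** Missed deaths = 762 × p × m, where p is 30-day mortality. With p = 2% and m = 20%: 762 × 0.02 × 0.20 = 3.0. With p = 5% and m = 60%: 762 × 0.05 × 0.60 = 22.9. The assumed ranges span about 3 to 23 deaths.

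**7. Primary endpoint.** Section 5.1 limits post-discharge DOT to the plan at discharge and excludes DOT from readmissions. Events unseen after discharge do not enter it in this way.

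**The case against.** The best defence is that passive follow-up to day 30 is planned. Section 5.2 rules out follow-up with patients, not follow-up of their records. Extracts, the chart review after day 30 and a sample check of outcomes against the electronic record are all specified. A death, ICU stay or readmission that reaches those records would be ranked correctly. This stands: a reader might infer that nothing is followed after discharge, and the protocol does not support that.

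A reader might also infer that unknown status is scored as Alive. No such rule exists. Rank 1 is the likely default, because Table 3 offers nothing else and all randomized patients are analysed, but the SAP may say otherwise. Ranking rules for unknowns belong there, and their absence from the protocol is not counted as an error. What an SAP cannot do is recover a date that the chart review never collected.

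The mortality conflict may be leftover wording. The same sentence in 3.1.3 speaks of control units, which does not fit individual randomization, and Section 5.1 refers the reader to Section 7 for definitions. That makes the intended window fairly clear, but the two statements still need reconciling.

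Three limits also stand. The documents do not say whether local charts show outside encounters or vital status. Readmission, read literally, may mean return to the same hospital, so an admission elsewhere may not be a missed event at all. Unequal loss is conditional: Section 3.1.1 hypothesizes equivalent length of stay.

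**Conclusion.** The point holds in a limited form. Two inconsistencies are in the text: in-hospital against 30-day mortality, and a readmission window that outlasts the reviewed window by the days from randomization to discharge. Beyond that, the 30-day outcomes apart from readmission are defined without a hospital limit but ascertained only from records, so events outside those records can be missed.

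The direction under equal loss is clear: absolute differences shrink toward zero while risk ratios do not change. Under unequal loss the bias can go either way, and it depends on length of stay or capture differing by arm. The size cannot be stated, because every rate in the illustrations is assumed. It would go too far to say that the trial cannot report 30-day mortality; it can report documented 30-day mortality. The issue concerns the safety and DOOR/RADAR results and is worth correcting, but it does not touch the primary DOT comparison in this way.

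**What to change.** 1. Reconcile 3.1.3, Section 7 and Appendix 4 on one mortality definition. Report in-hospital death and documented 30-day death separately.
2. Describe the 30-day outcomes as documented in the study hospital's record.
3. Align the readmission and chart-review windows, either by counting readmission to day 30 from randomization or by extending the review to 30 days after discharge.
4. Add a field for the date last documented alive to the chart review already planned, and report by arm the share with known day-30 status.
5. Add a DOOR sensitivity analysis, in the SAP if preferred, that treats unknown status the same way in both arms or uses a tipping-point approach across both. Ranking only the intervention arm's unknowns unfavourably would build in apparent harm, particularly if many discharged patients have no later record entry.

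The cost is one data field, one sensitivity analysis and wording changes, plus a somewhat later review if the second option in item 3 is taken. No patient contact is needed, so the waiver-of-consent design is unaffected. The fix recovers no outside event; it shows how much is unknown and leaves a weaker claim about 30-day mortality.

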## **6 STUDY PRODUCT DESCRIPTION**

Not applicable

### **6.1 Concomitant Medications/Treatments**

Not applicable

## 7 ASSESSMENT OF SAFETY

All randomized patients will undergo safety evaluation.

1. Specifications of safety parameters –Data will be collected on the adverse outcomes described in the Desirability of Outcome Ranking (DOOR) in Table 3 and three other safety outcomes:
  - a. C. difficile infection (CDI) – positive *C. difficile* stool test during the 30 days following randomization. Results from either PCR or ELISA tests are acceptable
  - b. Clinically significant deep venous thrombosis (DVT) – diagnosis of a new DVT during the 30 days following randomization that requires anticoagulation. A radiographic finding (via ultrasound, CT, or MRI) will be required for this diagnosis.
  - c. Readmission – return to the hospital within 30 days of hospital discharge
  - d. Relapse of suspected sepsis – restart or escalation of antibiotic therapy coupled with repeat blood cultures (+/- 24 hours of changed in antibiotic therapy) during the 30 days following randomization.
  - e. Acute kidney injury requiring hemodialysis – new onset acute kidney injury requiring 1 or more hemodialysis sessions during the 30 days following randomization.
  - f. Transfer to Intensive Care Unit (ICU) – admission or transfer to any intensive care unit within 30 days of randomization.
  - g. Death – within 30 days of randomization.
  - h. Number of hospital days (Length of Stay) starting on the day of randomization and up to 30 days post randomization.
  - i. Re-initiation of antibiotic therapy after >48 hours of no antibiotics within 30 days of randomization.
  - j. Need for new PICC line insertion within the 30 days of randomization.
2. Methods and timing for assessing, recording, and analyzing safety parameters – Local study personnel will be responsible for assessing and recording safety parameters. Duke study personnel will be responsible for monitoring safety through interaction with study site PIs and the Independent Monitor.
3. Guidelines for determining causality – causality will not be assessed, as the DOOR outcome is intended to reflect global patient outcomes.
4. Reporting procedures (for AE) – all safety parameters will be entered into the REDCap database. Data on safety parameters will be reviewed by the Independent Monitor and discussed with the central study team.

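### Readmission runs to 30 days after discharge, but the other six DOOR components and the stated chart review stop at 30 days after randomization

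*Protocol*

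**What the plan says.** Table 3 (Section 5.1) places "Readmission, relapse of suspected sepsis", *C. difficile* infection and deep venous thrombosis in rank 2. Two or more of these give rank 3. ICU admission and hemodialysis fill ranks 4 and 5, and death is rank 6. The secondary endpoint list sends the reader to Section 7 for the definitions.

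Section 7 counts readmission as "Readmission – return to the hospital within 30 days of hospital discharge", and the expected-AE list in Appendix 4 uses the same wording. The other components are tied to randomization:
- *C. difficile*: "stool test during the 30 days following randomization"
- Thrombosis: "diagnosis of a new DVT during the 30 days following randomization that requires anticoagulation"
- Sepsis relapse: "24 hours of changed in antibiotic therapy) during the 30 days following randomization"
- Death: "Death – within 30 days of randomization"
- Hemodialysis and ICU transfer: also limited to 30 days after randomization

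On ascertainment, Appendix 4 states "AEs are identified by chart review after 30-days post randomization for the 30-day time period following randomization". Its data analysis section has local staff assess and record safety parameters over the same 30 days. The primary endpoint definition in Section 5.1 says that DOT from readmissions in the 30 days after randomization is left out of the primary endpoint but enters the adverse-event measurement. The synopsis gives participation as 30 days, and Section 5.2 plans no specific patient follow-up after discharge.

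**The concern.** DOOR is one ordinal scale, and a patient's rank should describe one period. Here a single component runs on a later clock than the rest, and that clock outlasts the review that is meant to find the events. Two things can go wrong for a late readmission:

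- The site stops at day 30 as Appendix 4 directs. The patient then keeps a better rank than the definition of readmission allows.
- The readmission is found and counted. The patient then moves from rank 1 to 2 (or 2 to 3), but a more serious event in the same stay is ignored because its own window has closed.

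Local personnel assess these outcomes, so sites could also resolve the conflict differently. DOOR/RADAR is the first-listed secondary endpoint and is formally compared between arms (Section 9.4.1). Readmission is also a line in the table that the Independent Monitor reviews.

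**Working it through.** The protocol states no figure here that could be reproduced, so the check sets the windows side by side and then sizes the gap.

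**Windows, in days from randomization, with discharge on day L**

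| Item | Ends on day | Source |
|---|---|---|
| *C. difficile*, DVT, sepsis relapse, hemodialysis, ICU transfer, death | 30 | Section 7; Appendix 4 |
| Readmission | 30 + L | Section 7; Appendix 4 |
| Chart review for AEs | 30 | Appendix 4, Collection and Reporting |
| Recording of safety parameters | 30 | Appendix 4, Data Analysis Plans |
| Readmissions as described with the primary endpoint | 30 | Section 5.1 |

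Nothing in the protocol reconciles the second row with the others.

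**Share of the window outside the review.** The readmission window has 30 days, of which L fall after day 30, so for L up to 30 the share is L/30. The protocol does not report time from randomization to discharge, so L is assumed:
- L = 3: 3/30 = 10%
- L = 10: 10/30 = 33%

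**Share of events.** Window time is not the same as events. Assume a readmission probability p over the 30 days after discharge and a constant hazard h = −ln(1 − p)/30. The share of those readmissions that fall after day 30 is

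[exp(−h(30 − L)) − exp(−30h)] / p.

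With p = 15%, also assumed:
- L = 3: (0.8639 − 0.85)/0.15 = 9.3%
- L = 10: (0.8973 − 0.85)/0.15 = 31.5%

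Over p = 10% to 25% the share is 8.8% to 9.5% at L = 3 and 30.2% to 32.2% at L = 10, so L/30 is a fair approximation. If all 762 planned patients were discharged alive on day L, p = 15% would give about 11 affected patients at L = 3 and 36 at L = 10. These counts only illustrate scale.

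**Example of the mixed clocks.** A patient is discharged on day 10, readmitted on day 35, moved to ICU, and dies on day 38. Readmission is open until day 40, while ICU transfer and death closed on day 30. With no other event, the patient is rank 2 if the readmission is captured and rank 1 if it is missed.

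**The case against.** **Late readmissions might not be lost.** Section 5.1 plans electronic extracts for the primary and secondary outcomes, with further endpoints taken from billing, administrative and laboratory data. No end date is given. A reader might infer that readmissions after day 30 will certainly be missed; the protocol does not show that. This point stands. It answers only the missed events, however: a late readmission that the extract finds is still ranked without the ICU transfer or death that accompanies it.

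**The discharge anchor is not itself unfair between arms.** A reader might infer that counting from discharge, a date the intervention could move, biases the comparison. As defined, every patient discharged alive gets the same 30-day readmission window whatever the length of stay. Observable time differs by arm only if ascertainment stops at day 30 and length of stay differs, and the third secondary hypothesis in Section 3.1.1 expects equivalent length of stay. A window closed at day 30 after randomization has the opposite property: time at risk is 30 − L days, so earlier discharge means longer exposure. This stands as a cost of the fix.

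**A common window does not rescue the example patient.** With readmission also cut at day 30, the patient who dies on day 38 becomes rank 1. The gain is that all components are truncated at the same day, not that this patient's rank is truer.

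**Frequency is unknown.** The protocol gives no readmission rate, so it does not support a claim that readmission is among the commonest DOOR events.

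**Conclusion.** The conflict is real and lies in the protocol's own text. Readmission ends on day 30 + L, while the other six DOOR components, the chart review and the recording period end on day 30. Section 5.1 already speaks of readmissions over the shorter period. About L/30 of the readmission window is affected (10% at L = 3, 33% at L = 10), on assumed values of L. The number of patients cannot be derived from the protocol.

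The effect is confined to DOOR/RADAR, the readmission safety outcome and the Independent Monitor's table. The primary endpoint is unaffected, because DOT from readmissions is excluded from it. Neither certain loss of events nor a demonstrated bias between arms is supported. The point is that definition and ascertainment disagree inside a formally tested ordinal endpoint, and that a wording change can align them.

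Section 3.1.3 has a minor related slip: "including in-hospital mortality, length of stay, and subsequent ICU transfer compared to eligible patients in control units". Section 7 uses death by day 30, and individual patients, not units, are randomized. Section 7 leaves the DOOR definition of death clear, so this is clerical.

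**What to change.** 1. In Section 7 and Appendix 4, for DOOR and for the monitor's table, define readmission as a return to hospital after index discharge and within 30 days of randomization. This matches the existing review and recording period and the language of Section 5.1, and all ranks then refer to the same 30 days.
2. State the limitation beside the definition: later readmissions are not counted, and time at risk is 30 − L days, so it depends on length of stay. Present readmission together with hospital days in the 30 days after randomization, which is already a secondary outcome.
3. If readmission within 30 days of discharge is also wanted, report it as a separate outcome from the electronic extracts, and state that the extract period runs to discharge plus 30 days.
4. In Section 3.1.3, align the mortality wording with death within 30 days of randomization, and refer to the control arm.

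Items 1, 2 and 4 need wording changes only and fit the chart review already planned. Item 3 needs an extract period long enough to cover the last patient's post-discharge window. The scientific cost is the readmissions between day 31 and day 30 + L, which leave DOOR and are kept only if item 3 is adopted.
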